5.3 Inclusion Criteria

1. Able and willing to comply with the protocol and provide written informed consent prior to study-specific screening procedures
2. Able and willing to adequately and consistently perform spirometry as required by the protocol
3. Able and willing to participate in standardized airway clearance techniques
4. Confirmed diagnosis of CF as defined by iontophoretic pilocarpine sweat chloride test (sweat chloride) of > 60 mmol/L
5. Confirmation of cystic fibrosis transmembrane conductance regulator (CFTR) gene mutations homozygous for the $\Delta F508$ mutation. Genetic testing performed prior to the year 2000 must be re-confirmed.
6. Male or female 18 to 60 years of age
7. Body mass index (BMI) of ≥ 17 kg/m²
8. Non-smoking for a minimum of two years, including cigarettes, cigars, and e-cigarettes
9. Stable pulmonary symptoms associated with CF
10. Creatinine clearance > 60 mL/min, as calculated by Cockcroft-Gault equation based on actual body weight

11. A. Women of childbearing potential must agree to use a highly effective method of birth control (defined as those, alone or in combination, that result in a low failure rate [ie, less than 1% per year]). See Section 6.3.3 for a list of highly effective methods of birth control.
11. B. Men must agree to use barrier contraception (ie, condoms) except when infertility is documented (eg, bilateral orchidectomy or azospermia and/or infertility secondary to CF)
12. FEV₁ ≥ 70% of predicted normal for age, gender, and height (post-bronchodilator value using NHANES III standards) at screening
13. Stable lung function determined by the treating physician, provided FEV₁ at Day -1 is within 10% of FEV₁ at screening.

NOTE: Eligibility criteria 14 through 20 relate to acceptable laboratory values at screening. Subjects with a screening laboratory value outside the specified range may be permitted if the value is not clinically significant in the opinion of the Investigator, with concurrence from the Sponsor's Medical Monitor.

14. Total WBC ≤ 12,000/μL
15. Hemoglobin > 10 g/dL
16. Hematocrit > 30%
17. Platelet count between 150 and 450 x 10³/μL
18. Prothrombin time, international normalized ratio (INR) and partial thromboplastin time within normal limits
19. Serum albumin > 2.5 g/dL at screening
20. Liver function tests within 2X the upper limit of normal (SGPT/ALT, SGOT/AST, GGT, alkaline phosphatase, bilirubin [total and direct])

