6.1.8 Premedication

For subjects whose standard CF medications include a short-acting β -agonist (SABA), the SABA should be administered within 15 minutes to 2 hours prior to the first study drug dose. If no adverse reaction occurs with the first dose, subsequent doses need not be preceded by a SABA, as determined by the Investigator.

For those subjects whose standard CF medications include a long-acting β -agonist (LABA), the LABA should be administered between 1 and 4 hours prior to each study drug dose.

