6.3 Concomitant Medications and Ancillary Therapy

6.3.1 Permitted Concomitant Medications

All concurrent CF therapies should be continued for the duration of the study. Prior to study drug dosing on a given day, the following order of concurrent treatment should be adhered to: Long- and/or Short acting bronchodilator, mucolytic therapy (eg, Pulmozyme), chest physiotherapy (airway clearance technique), inhaled corticosteroid, inhaled antibiotics.

Subjects who are prescribed chronic, intermittent inhaled antibiotics should participate in the study when they are most stable and continue the inhaled antibiotic throughout the study. For most patients, this would mean that the subject initiates the inhaled antibiotic during the screening period and continues taking it as prescribed through the end of study, including some additional days or weeks. As the regimens of chronic inhaled antibiotics varies significantly from patients to patient, the Investigator is encouraged to discuss with the Sponsor's Medical Monitor the appropriate regimen for the course of the study.

Ancillary therapy regimens and airway clearance techniques should remain consistent throughout the study period. Other ancillary therapy may be administered at the discretion of the Investigator. Subjects should receive full supportive care, including antibiotics, antiemetics, bronchodilators, etc., as appropriate. The reason(s) for ancillary therapy, including dosage and date(s) of treatment, will be recorded in the source documents.

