7.4.3 Week 1, Day 1 (Dose 1)

Pre-dose:

1. Subject self-completes the CFQ-R prior to all other procedures and assessments
2. Symptom directed physical examination (including body weight)
3. Vital signs
4. Oximetry
5. Concomitant medications review
6. AE review
7. Administer any routine pulmonary medications and airway clearance techniques, including SABA and/or LABA, Pulmozyme, inhaled corticosteroids and/or antibiotics
8. Initiate continuous cardiac and vital signs monitoring and continue for 12 hours post dose
9. Spirometry (FEV₁, FVC, and FEF₂₅₋₇₅), post administration of short-acting bronchodilator
10. Obtain blood samples for local laboratory assessments
11. Obtain urine sample for urinalysis (Time 0/pre-dose)
12. Obtain blood and urine samples for PK (Time 0/pre-dose)

Study Drug Administration:

Study drug to be administered by qualified site personnel via the designated study nebulizer, until all study drug solution has been administered. Subjects are to be seated during the entire

duration of study drug administration, inhaling the nebulized study drug using normal tidal breathing (no noseclips). Details regarding study drug preparation, device preparation and handling, as well as administration of study drug will be included in the Pharmacy Manual and Study Manual.

Post-dose:

1. Symptom-directed physical examination at 15, 60 minutes, 2, 4, 6, 8, and 12 hours post dose
2. Vital signs at 1, 10, 30, 60 minutes, 2, 4, and 12 hours post dose
3. Oximetry at 1, 10, 30, 60 minutes, 2, 4, and 12 hours post dose
4. Concomitant medications review
5. AE review
6. Spirometry at 10, 30, and 60 minutes, and 2, 4, and 8 hours post dose
7. Obtain blood samples for local laboratory assessments at 30, 60 minutes, 2, 4, 8, and 12 hours post dose
 - Complete blood count (CBC) with absolute differential
 - Serum chemistry
8. Obtain the following samples for PK:
 - Blood at 0.5, 1, 2, 3, 4, 12 hours post dose
 - Pooled urine from 0 to 4 hours and 4 to 12 hours post dose. Subjects should empty their bladders just prior to dosing and at the end of each time interval for the final urine collection of that interval. Urinalysis by dipstick will be performed on the pooled urine samples for each time interval.
 - Sputum at 3 times post dose, within the first 6 hours post dose. Suggest obtaining samples in conjunction with performing spirometry at 10, 60 minutes, and 4 hours post dose.
9. Discharge subject

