7.4.4 Week 1, Day 3 (Dose 2)

Pre-dose:

1. Symptom-directed physical examination
2. Vital signs
3. Oximetry
4. Concomitant medications review
5. AE review

6. Administer any routine pulmonary medications and airway clearance techniques, including SABA and/or LABA, Pulmozyme, inhaled corticosteroids and/or antibiotics
7. Obtain blood for PK sample prior to dosing (approximately 48 hours post dose 1)
8. Administer study drug

Post-dose:

1. Symptom-directed physical examination at 15, 60 minutes, 4, 8, and 12 hours post dose
2. Vital signs at 1, 10, 30, 60 minutes, 2, 4 and 12 hours post dose
3. Oximetry at 1, 10, 30, 60 minutes, 2, 4 and 12 hours post dose
4. AE review
5. Spirometry at 20, and 60 minutes, and 4 hours post dose
6. Obtain blood samples for local laboratory assessments at 60 minutes and 4 hours post dose
 - Complete blood count (CBC) with absolute differential
 - Serum chemistry
7. Obtain urine sample for local urinalysis at 60 minutes and 4 hours post dose
8. Obtain blood sample for PK at 2 hours post dose
9. Discharge subject

7.4.5 Week 1, Day 4

1. Symptom-directed physical examination
2. Vital signs
3. Oximetry
4. Concomitant medications review
5. AE review
6. Spirometry
7. Obtain blood and urine samples for local laboratory assessments
8. Obtain blood and sputum samples for inflammatory biomarkers
9. Obtain the following samples for PK (approximately 72 hours post dose 1):
 - Blood, urine, and sputum

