7.4.12 Follow-up Visits—7 and 28 Days After Last Dose

Follow-up visits will occur 7 and 28 days after the last dose of study drug (dose 12).

If at any time during the study the subject discontinues the study early, the subject should return to the clinic to complete the End of Treatment Visit procedures below, and should also return to the clinic to complete the End of Study Visit procedures 28 days after the last study drug dose.

7.4.12.1 7 Days After Last Dose—End of Treatment Visit

1. Subject self-completes the CFQ-R prior to all other procedures and assessments
2. Complete physical examination (including body weight)
3. Vital signs
4. Oximetry
5. Concomitant medication review
6. AE review
7. Chest Xray
8. 12-lead ECG
9. Spirometry
10. Obtain blood and urine samples for local laboratory assessments
11. Obtain urine or blood for pregnancy test (for women of child-bearing potential)
12. Obtain blood samples for PK
13. Obtain sputum sample for the following local laboratory assessment:
 - Microbiology organism identification
14. Obtain blood and sputum samples for inflammatory biomarkers
15. Obtain sample for sweat chloride determination

7.4.12.2 28 Days After Last Dose—End of Study Visit

1. Subject self-completes the CFQ-R prior to all other procedures and assessments
2. Complete physical examination (including body weight)
3. Vital signs
4. Oximetry
5. Concomitant medication review
6. AE review
7. Spirometry
8. Obtain blood and urine samples for local laboratory assessments
9. Obtain urine or blood for pregnancy test (for women of child-bearing potential)
10. Obtain blood and sputum samples for inflammatory biomarkers

11. Obtain serum samples for PK
12. Obtain sample for sweat chloride determination

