8.10 Pulmonary Function

Spirometry will be performed per American Thoracic Society (ATS)/European Respiratory Society (ERS) Standards. FEV₁, FVC, and FEF₂₅₋₇₅ will be collected. Actual liter values will be recorded. Prior to study drug dosing on a given day, the following order of concurrent treatment should be adhered to: Long- and/or Short acting bronchodilator, mucolytic therapy (eg,

Pulmozyme), chest physiotherapy (airway clearance technique), inhaled corticosteroid, inhaled antibiotics. Ancillary therapy regimens and airway clearance techniques should remain consistent throughout the study period, and the order of therapies and medications should also remain the same.

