9.0 OTHER CONSIDERATIONS

9.1 Routine CF Pulmonary Medications

Administer any routine pulmonary medications, including SABA and/or LABA, Pulmozyme, and inhaled corticosteroids and/or antibiotics, in the same order each dosing day, prior to spirometry and study drug dosing, during the in-house phase of the study.

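### MAD baseline FEV1 is measured after a short-acting bronchodilator, but spirometry on Days 4, 33 and 54 has no bronchodilator step, so within-subject falls there can be overstated

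*Protocol*

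**What the plan says.** **Baseline.** For the MAD cohorts, the Day -1 and Day 1 pre-dose spirometry lines (protocol 7.4.2 and 7.4.3) both carry the condition "post administration of short-acting bronchodilator". Inclusion criterion 12 also uses a "post-bronchodilator value using NHANES III standards" at screening. SAP 4.2.1 and SAP Table 7 take the latest value before the first dose as baseline, so the MAD baseline FEV1 is specified as post-bronchodilator.

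**Non-dosing visits.** Day 4 (7.4.5) and the visits 7 and 28 days after the last dose, Days 33 and 54 (7.4.12.1 and 7.4.12.2), list spirometry without a bronchodilator condition. None of them has a step for giving routine pulmonary medication.

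**General rules.**
- 6.3.1: "Ancillary therapy regimens and airway clearance techniques should remain consistent throughout the study period".
- 8.10 adds that "the order of therapies and medications should also remain the same". The sequence it sets out is tied to study drug dosing.
- 9.1 has routine pulmonary medications given "in the same order each dosing day, prior to spirometry and study drug dosing, during the in-house phase of the study".
- 6.1.8, for subjects whose standard treatment includes a short-acting beta-agonist (SABA): "If no adverse reaction occurs with the first dose, subsequent doses need not be preceded by a SABA, as determined by the Investigator".

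**Use of the readings.** SAP 4.8.2.1 includes Days 4, 33 and 54 in the mixed model for change in ppFEV1. SAP 4.10.1.4 counts subjects whose FEV1 falls at least 15% from baseline, at any time and by visit. Protocol 5.5.3.2 ends dosing permanently for such a fall. Protocol 4.3 sends the data to the DSMC before escalation if two or more subjects in a cohort have one.

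**The concern.** Change from baseline is interpretable within a subject only if both readings are taken in the same bronchodilator state. A site that follows the visit lists as written compares a post-bronchodilator baseline with a reading on Day 4, 33 or 54 whose bronchodilator state is uncontrolled. Any mismatch tends in one direction: effect present at baseline and absent later looks like a loss of lung function.

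The exposed uses are mainly safety uses. Day 4 falls between doses 2 and 3, so a false 15% fall there could end dosing after 2 of 12 doses, with no resumption allowed. Readings on Days 4 and 33 fall within the follow-up that the DSMC reviews before escalation (4.2), so they can count towards its trigger. One mismatched reading can put a subject in the 15% table. The by-dose descriptive changes, in planned groups of six active subjects, would shift downwards.

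**Working it through.** **Step 1. MAD baseline and non-post-dose spirometry, visit by visit.**

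| Visit | Protocol section | Medication step before spirometry | Post-SABA condition on the spirometry line |
|---|---|---|---|
| Day -1 | 7.4.2 | None | Yes |
| Day 1 pre-dose | 7.4.3 | Routine medications | Yes |
| Day 5 pre-dose | 7.4.6 | Routine medications | No |
| Days 8, 15, 22 pre-dose | 7.4.7 | Routine medications | No |
| Day 26 pre-dose | 7.4.9 | Routine medications | No |
| **Day 4** | 7.4.5 | None | No |
| **Day 33** | 7.4.12.1 | None | No |
| **Day 54** | 7.4.12.2 | None | No |

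On dosing days with pre-dose spirometry, routine SABA users are largely covered, because the routine-medication step comes first. The three non-dosing visits have neither safeguard.

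**Step 2. Do the general rules fill the gap?** Section 9.1 covers dosing days in the in-house phase, so it does not reach these visits. The sequence in 6.3.1 and 8.10 applies before study drug dosing. Their consistency sentences cover regimen and order of therapies, not whether a SABA precedes spirometry or by how long.

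**Step 3. Share of the SAP model.** SAP 4.8.2.1 lists these post-baseline time points: Day 3 pre-dose, Day 4, Day 5, Day 8, Day 15, Day 22 and Day 26 pre-dose, Day 26 at 4 hours, Day 33 and Day 54. That is 10, and 3 of them are the uncovered visits. Days 33 and 54 are 2 of the 4 points at which placebo differences are estimated. Protocol 7.4.4 does not schedule pre-dose spirometry on Day 3, so on the protocol's schedule the count is 3 of 9 (10 - 1).

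**Step 4. Size, as illustration only.** Neither document gives a bronchodilator response, so there is no plan figure to reproduce. Let b be the fraction of baseline FEV1 lost because the bronchodilator effect is absent. The range b = 0 to 12% is an assumption.

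- Real further fall d that reads as 15%: (1 - b)(1 - d) = 0.85, so d = 1 - 0.85/(1 - b).
- Spurious change in ppFEV1 points: b x baseline ppFEV1, shown at 70 (the eligibility minimum) and 90 (the subgroup cut in the post hoc SAP).

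| b | d reading as 15% | Points at baseline 70 | Points at baseline 90 |
|---|---|---|---|
| 0% | 15.0% | 0 | 0 |
| 2% | 13.3% | 1.4 | 1.8 |
| 5% | 10.5% | 3.5 | 4.5 |
| 8% | 7.6% | 5.6 | 7.2 |
| 10% | 5.6% | 7.0 | 9.0 |
| 12% | 3.4% | 8.4 | 10.8 |

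The number of mismatched subjects is also unknown. With k of 6 mismatched, the group mean moves by k/6 of the last two columns. At b = 5% and baseline 90 that is 0.75 points for k = 1, 2.25 for k = 3 and 4.5 for k = 6.

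**The case against.** The best defence is that the protocol handles bronchodilators consistently in practice. Routine SABA users receive their medication before pre-dose spirometry on dosing days, all CF therapies continue throughout, and 8.10 asks for constant regimens and order. Spirometry follows ATS/ERS standards, 7.1 refers timing windows to a Laboratory Manual, and a Study Manual exists. Neither manual was available for this review, and either may settle the point. Concomitant medications are already reviewed on Days 4, 33 and 54. This narrows the concern to three visits. It does not close it, because nothing in the protocol fixes bronchodilator state there.

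The size is open to fair attack: both the response and the number of mismatched subjects are assumed, and the range includes no effect. That objection stands.

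A reader might infer more than the documents support:
- *All follow-up spirometry is off bronchodilator.* The routine-medication steps on dosing days contradict this.
- *6.1.8 conflicts with 7.4.* It allows the SABA to be omitted after the first dose, but a site can satisfy both sections by giving it.
- *Every subject without a routine SABA is mismatched.* This holds only if 7.4.2 and 7.4.3 require a SABA for everyone. They can also be read as setting the sequence for routine users, since 6.1.8 limits SABA premedication to them.
- *The drug-placebo difference is biased.* Both randomised arms follow the same visit schedule, subjects and site staff other than the pharmacist are blinded, and related reactions of Grade 2 or higher end dosing. No systematic bias is expected, so the point shifts above should not be set against the SAP's effect sizes of 3, 5 and 7, which are differences from placebo.

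**Conclusion.** The gap is real at Days 4, 33 and 54 and is a cheap improvement, not a major flaw. Within-subject FEV1 change at those visits can include lost bronchodilator effect and tends towards false falls.

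Its reach is limited. The stopping rule is exposed through these visits only at Day 4, because Days 33 and 54 follow the last dose. The DSMC reviews every cohort in any case, so the effect on its trigger is mainly on what it sees. FEV1 efficacy is exploratory (protocol 4.1.3), and errors tend towards caution. The 15% table and the by-dose descriptive changes are exposed at all three visits.

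The documents support the direction but not a magnitude. The conclusion assumes that the unseen manuals do not already fix bronchodilator state at these visits, and that at least some subjects have a measurable SABA effect at baseline that is absent later.

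**What to change.** In protocol 7.4.5, 7.4.12.1, 7.4.12.2 and 8.10, require spirometry on Days 4, 33 and 54 in the same bronchodilator state as that subject's Day 1 pre-dose baseline: post-SABA if the baseline was post-SABA, with a similar interval since the dose. Record the time of the last SABA or LABA at those visits.

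Three things should not be changed or added:
- Do not extend the rule to post-dose serial spirometry. The readings after the first dose are there to detect provoked bronchospasm (synopsis), and extra SABA could mask it.
- Leave the 6.1.8 option alone. Removing it would force premedication before later doses and hide tolerability without a SABA.
- Do not add an analysis that excludes mismatched readings. SABA use after randomisation could be affected by treatment, so exclusion could bias a placebo contrast that is not otherwise expected to be biased, and it would thin groups of six.

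The cost is one SABA dose or timing check at three visits, a few lines of protocol text and at most one CRF field.

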7.4.4 Week 1, Day 3 (Dose 2)

Pre-dose:

1. Symptom-directed physical examination
2. Vital signs
3. Oximetry
4. Concomitant medications review
5. AE review

6. Administer any routine pulmonary medications and airway clearance techniques, including SABA and/or LABA, Pulmozyme, inhaled corticosteroids and/or antibiotics
7. Obtain blood for PK sample prior to dosing (approximately 48 hours post dose 1)
8. Administer study drug

Post-dose:

1. Symptom-directed physical examination at 15, 60 minutes, 4, 8, and 12 hours post dose
2. Vital signs at 1, 10, 30, 60 minutes, 2, 4 and 12 hours post dose
3. Oximetry at 1, 10, 30, 60 minutes, 2, 4 and 12 hours post dose
4. AE review
5. Spirometry at 20, and 60 minutes, and 4 hours post dose
6. Obtain blood samples for local laboratory assessments at 60 minutes and 4 hours post dose
 - Complete blood count (CBC) with absolute differential
 - Serum chemistry
7. Obtain urine sample for local urinalysis at 60 minutes and 4 hours post dose
8. Obtain blood sample for PK at 2 hours post dose
9. Discharge subject

7.4.5 Week 1, Day 4

1. Symptom-directed physical examination
2. Vital signs
3. Oximetry
4. Concomitant medications review
5. AE review
6. Spirometry
7. Obtain blood and urine samples for local laboratory assessments
8. Obtain blood and sputum samples for inflammatory biomarkers
9. Obtain the following samples for PK (approximately 72 hours post dose 1):
 - Blood, urine, and sputum

7.4.6 Week 1, Day 5 (Dose 3)

Pre-dose:

1. Symptom-directed physical examination
2. Vital signs
3. Oximetry
4. Concomitant medications review
5. AE review
6. Administer any routine pulmonary medications and airway clearance techniques, including SABA and/or LABA, Pulmozyme, inhaled corticosteroids and/or antibiotics
7. Spirometry (FEV₁, FVC, and FEF₂₅₋₇₅)
8. Obtain blood sample for PK (approximately 96 hours post dose 1)
9. Administer study drug

Post-dose:

1. Symptom-directed physical examination at 15, 60 minutes, and 2 hours post dose
2. Vital signs at 1, 10, 30, 60 minutes, and 2 hours post dose
3. Oximetry at 1, 10, 30, 60 minutes, and 2 hours post dose
4. AE review
5. Spirometry at 20, and 60 minutes, and 4 hours post dose (if FEV₁ at 60 minutes was decreased 15% from pre-dose value)

7.4.7 Weeks 2, 3 and 4 (Doses 4, 7, and 10)

Pre-dose

1. Subject self-completes the CFQ-R prior to all other procedures and assessments (Week 3 dose 7 only)
2. Complete physical examination (including body weight)
3. Vital signs
4. Oximetry
5. Concomitant medications review
6. AE review
7. Administer any routine pulmonary medications and airway clearance techniques, including SABA and/or LABA, Pulmozyme, inhaled corticosteroids and/or antibiotics

8. Spirometry (FEV₁, FVC, and FEF₂₅₋₇₅)
9. Obtain blood and urine samples for local laboratory assessments
10. Obtain blood sample for PK
11. Obtain pre-dose sputum sample for PK (prior to dose 4 only). Suggest obtaining sample in conjunction with performing spirometry prior to dosing
12. Obtain blood and sputum samples for inflammatory biomarkers
13. Administer study drug

Post-dose:

1. Symptom-directed physical examination at 15, 60 minutes, 2 hours post dose
2. Vital signs at 1, 10, 30, 60 minutes, 2 hours post dose
3. Oximetry at 1, 10, 30, 60 minutes, 2 hours post dose
4. Concomitant medications review
5. AE review
6. Spirometry at 20, and 60 minutes post dose
7. Obtain blood samples for local laboratory assessments at 15, 60 minutes, 2 hours post dose
8. Obtain blood for PK at 1 hour post dose 7 only
9. Obtain urine sample for urinalysis at 60 minutes and 2 hours post dose

